Study protocol

Diaphragmatic and sternocleidomastoid muscle recruitment at various inspiratory loads with and without breathing instruction in healthy adults

Objectives

- (1) to investigate the relationship between sternocleidomastoid muscle recruitment and diaphragm thickness fraction during increasing inspiratory resistance in healthy adults.
- (2) to compare diaphragmatic and sternocleidomastoid muscle recruitment patterns with and without a standard diaphragmatic breathing instruction with increasing inspiratory resistance in healthy adults.

Method

Ethical committee approval

Ethical committee approval was granted by the Research Ethics Committee of Hong Kong Metropolitan University (ethics approval number: HE-OT2023/13).

Sample size calculation

Sample size will be determined by repeated-measures analysis of variance (ANOVA) using G*Power 3.1. Considering an effect size of 0.3, an alpha error probability of 0.05, a power of 0.80, the estimated sample size is 30 participants. An additional 20% of the cohort will be recruited to compensate for the predicted sample size attrition. The final estimated sample size will be at least 36 participants.

Participants

Participants ≥ 18 years of age with normal health will be recruited and screened for any of the following ‘exclusion’ criteria: (1) participants with known cardiovascular, pulmonary, musculoskeletal or psychiatric disorders; (2) pregnancy; (3) with respiratory symptoms (from flu or other respiratory infection during the 2 weeks prior to measurements).

Procedure

Upon arrival at the laboratory, eligible participants will first perform a standard spirometry lung function test. The maximum inspiratory pressure (MIP) will be determined with a pressure

threshold inspiratory loading device (POWERbreathe, K₂). Each participant will then be instructed to use the device to perform, in random order, 10 breaths at an inspiratory intensity of 30%, 40%, 50%, 60%, 70%, and 80% MIP. A rest period of 15 minutes will be allowed between each inspiratory pressure set of 10 breaths. Simultaneous surface electromyographic (sEMG) recording of the right sternocleidomastoid muscle and ultrasound of right diaphragmatic thickness will be conducted during each breath.

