The entire recording procedure will be repeated on a separate day. During the repeat measurements, participants will be provided with specific breathing instruction to focus on the use of the diaphragm and to inhale air to the lower part of the chest. Practice trials will be conducted to ensure participant's understanding of diaphragmatic breathing.

Measurements

Spirometry respiratory function

Forced vital capacity, forced expiratory volume in 1 second, and MIP will be measured following the American Thoracic Society guideline protocol.

Diaphragmatic contraction

During each of the 60 breaths, thickness of the right diaphragm at the end of each tidal expiration and at the end of each forced inspiration will be measured using diaphragmatic ultrasonography (Mindray M9, Shenzhen, China). The recorded thickness over each set of 10 breaths will be averaged. The strength of diaphragmatic contraction will be reflected by the diaphragmatic thickening fraction (DTf), which is calculated as a ratio of [the difference between mean diaphragmatic thickness at the end of each inspiratory pressure and mean diaphragmatic thickness at the end of tidal expiration / the diaphragmatic thickness at the end of tidal expiration] x100%.

Recruitment of the sternocleidomastoid muscle

A Noraxon Ultium wireless sEMG system (Noraxon USA, Inc., Scottsdale, AZ, USA) will be used to detect the muscle recruitment activity of the right sternocleidomastoid muscle. On the 2 days of data collection, sEMG data over each set of 10 breaths will be averaged for data analysis.

Self-perceived exertion level

Self-perceived exertion level at the end of each 10-breath set at each inspiratory pressure, will be also recorded using the Borg's scale of Rate of Perceived Exertion.

Statistical analysis

All data will be analyzed using the IBM SPSS Statistics for Windows, Version 25.0 (Armonk, NY: IBM Corp).

Changes in DTf, muscle activity of sternocleidomastoid and fatigue during each inspiratory protocol will be analyzed using repeated-measures ANOVA.

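### Objective 1 has no association analysis, and relating the per-load averages without a load term would mostly restate the shared load trend

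*Combined protocol and SAP*

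**What the plan says.** The document is the combined protocol and SAP.

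- **Objectives, item 1:** "to investigate the relationship between sternocleidomastoid muscle recruitment and diaphragm thickness fraction during increasing inspiratory resistance in healthy adults".
- **Procedure:** each participant takes "10 breaths at an inspiratory intensity of 30%, 40%, 50%, 60%, 70%, and 80% MIP", in random order. "Simultaneous surface electromyographic (sEMG) recording of the right sternocleidomastoid muscle and ultrasound of right diaphragmatic thickness will be conducted during each breath". A second session on another day repeats this with a breathing instruction.
- **Measurements, Diaphragmatic contraction:** end-expiratory and end-inspiratory thickness are measured on all 60 breaths, and then "The recorded thickness over each set of 10 breaths will be averaged". DTf is built from those averages, with numerator "the difference between mean diaphragmatic thickness at the end of each inspiratory pressure and mean diaphragmatic thickness at the end of tidal expiration". No breath-level DTf is defined.
- **Measurements, Recruitment of the sternocleidomastoid muscle:** "On the 2 days of data collection, sEMG data over each set of 10 breaths will be averaged for data analysis".
- **Statistical analysis:** repeated-measures ANOVA of the changes in DTf, sternocleidomastoid activity and fatigue. No correlation, regression or mixed model links the two muscles.

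**The concern.** Repeated-measures ANOVA of each outcome shows whether that outcome changes with load. It does not estimate how the two outcomes relate, so Objective 1 has no planned analysis. The natural repair would be to correlate or regress the set averages. Within a session, each person then has one pair at each of six loads, and the experimenter sets those loads. If both measures climb with load, they will correlate across loads whether, at a given load, the muscles work together, substitute for one another or are unrelated.

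At stake is the interpretation of Objective 1. A large positive coefficient could be reported as the relationship when it mainly says that both measures respond to load. The breath-level pairs that simultaneous recording provides play no part in the planned analysis.

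**Working it through.** **1. Counts.** 6 loads x 10 breaths = 60 breaths per session, as the protocol states. After averaging there are 6 pairs per person per session, one per load, so within a session there are no degrees of freedom within a person at a fixed load. The sample size section gives 30 x 1.20 = 36 participants. At 36, for one session:

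- Pairs: 36 x 6 = 216 averaged, 36 x 60 = 2,160 breath-level.
- Within-person, across loads: 36 x 5 - 1 = 179 df.
- Averages adjusted for person and load: 35 x 5 - 1 = 174 df. Detectable r at 80% power, two-sided 5%: tanh(2.80/sqrt(173)) = 0.21.
- Breaths within set: 36 x 6 x 9 - 1 = 1,943 df.

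The stated 30 and 36 were sized for ANOVA, and this point does not bear on them.

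**2. General form (assumed inputs).** Suppose load explains a share R2 of the within-person variance of each average, with the same trend in both, and the load-adjusted correlation of the averages is rho. The across-load correlation is then R2 + (1 - R2) x rho.

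| R2 | rho = -0.3 | rho = 0 | rho = +0.3 |
|---|---|---|---|
| 0.8 | +0.74 | +0.80 | +0.86 |
| 0.5 | +0.35 | +0.50 | +0.65 |

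**3. By variance component (all values assumed).** Standardise load to SD 1 over the six levels. Let b be the load slope of both measures, s the set-level SD, w the breath SD and m the measurement SD. Let rho_s and rho_b be the set-level and breath-level correlations. For a 10-breath average:

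- residual variance v = s² + (w² + m²)/10
- residual covariance c = rho_s x s² + rho_b x w²/10
- across-load r = (6b² + 5c)/(6b² + 5v)
- load-adjusted r = c/v
- within-set r = rho_b x w²/(w² + m²)

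Take b = 1, s = 0.3, rho_s = 0, w = m = 1. Then v = 0.09 + 0.20 = 0.29 and 5v = 1.45.

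| rho_b | across-load | load-adjusted | within-set |
|---|---|---|---|
| -0.3 | 5.85/7.45 = +0.79 | -0.03/0.29 = -0.10 | -0.3/2 = -0.15 |
| 0 | 6/7.45 = +0.81 | 0 | 0 |
| +0.3 | 6.15/7.45 = +0.83 | +0.10 | +0.15 |

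Simulation (400 runs, 30 participants) agrees: 0.787, 0.806 and 0.825 across loads. For rho_b = -0.3 it gives -0.103 load-adjusted and -0.151 within set. The across-load figure barely registers the sign.

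**4. Dependence on the load slope.** Take no coupling, person-to-person slope SD 0.5, s = 0.3, w = 0.5 and m = 0. The across-load r is 6b²/(6b² + 6 x 0.25 + 5 x 0.115) = 6b²/(6b² + 2.075). For b = 1, 0.5 and 0.25 this gives 0.74, 0.42 and 0.15. Adjusting the averages for person and load brings the simulated figure to about 0.00 in each case.

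**5. Limits of the breath-level figure.**

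- *Trade-off between sets.* With s = 0.5, rho_s = -0.5, rho_b = 0 and w = m = 1, the load-adjusted r is -0.125/0.45 = -0.28, while the within-set r is 0.00.
- *Shared breath effort.* Add effort SD e to both signals in the rho_b = -0.3 case of step 3. The within-set r is (-0.3 + e²)/(2 + e²), which is 0.00 at e = 0.55 and +0.08 at e = 0.7.
- *Noise.* A true breath-level -0.5 reads -0.25 at reliability 0.5 and -0.10 at reliability 0.2.

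**The case against.** The strongest reply is that Objective 1 is itself worded in terms of rising resistance. On that reading, across-load variation is the signal and not a confounder, and the protocol never mentions a fixed-load or breath-to-breath relationship. This stands to the extent that the across-load association is a legitimate target and should be reported. It does not supply an analysis of it, and the figure alone cannot separate joint recruitment from substitution.

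Second, averaging repeated ultrasound readings is a defensible way to reduce measurement error, and a load term removes the common load effect from the averages. Both statements are correct. A reader might infer that averaging forces a load-confounded answer, but the documents do not support that: load-adjusted averages keep 174 df at 36 participants. The trouble would come from leaving the load term out, and no association model, with or without one, is planned.

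Third, that load drives both measures is assumed. The planned ANOVA tests it, and with a shallow slope the artefact is small.

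Fourth, two sessions give two pairs per person per load. That contrast is mixed with day and breathing instruction, so it is not a clean reading of Objective 1.

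**Conclusion.** The concern holds in limited form. The plan names no analysis that answers Objective 1. If both measures rise with load, within-person association of the set averages without a load term would mostly reflect that shared rise. Under the assumptions in the working, the artefact with no coupling runs from about 0.15 (shallow slope) to about 0.8 (steep slope). At the steep end, a true breath-level correlation of -0.3 still reads +0.79.

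Two stronger readings are not supported. A reader might infer that the breath-level data are thrown away. The text says only that sEMG is averaged for analysis and thickness is averaged per set; nothing says that the records are deleted. A reader might also infer that breath-level pairs are the better or more powerful answer. Whether they are depends on where the coupling sits, on shared breath effort and on measurement reliability. The documents give no variances or reliability, and step 5 shows cases where the breath-level figure misses the coupling or takes the wrong sign.

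**What to change.** Keep the set averages for the ANOVAs. For Objective 1, pre-specify a mixed model of log sEMG on DTf. Compute DTf for each breath from its own two thicknesses and pair it with the sEMG of the same breath. Split DTf into three terms: the person mean, the set's deviation from the person mean, and the breath's deviation from its set mean. Include random effects for participant and set. Fit it separately by session, or with a session term. The person-mean term keeps differences between people out of the set-level estimate.

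Report three associations, each with a 95% CI:

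1. across-load within-person: the set-deviation term with load left out;
2. load-adjusted set-level: the same term with load as a categorical factor;
3. within-set: the breath-deviation term.

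The first and second need separate fits, because once load is a factor the set term is no longer the across-load association. Do not present the first alone as the relationship. Treat the third as supportive beside the second, and state that it is attenuated by measurement noise, may reflect shared breath effort and may miss trade-off between sets.

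The cost is analysis wording and some processing time to split the sEMG by breath. No extra measurements or participants are needed.

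### Repeated-measures ANOVA drops a participant's whole record for an outcome when one set is missing, and the 36 recruited leave no margin for scattered missing sets beyond the budgeted attrition

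*Combined protocol and SAP*

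**What the plan says.** - **Analysis.** In the Statistical analysis section, changes in diaphragmatic thickening fraction, sternocleidomastoid activity and fatigue "will be analyzed using repeated-measures ANOVA". The software is SPSS 25. The SPSS procedure and the ANOVA factors are not named. Nothing is said about missing sets, the analysis population or imputation.
- **Data structure.** Under Procedure, each participant does a 10-breath set at each of six loads, from 30% to 80% of MIP. "The entire recording procedure will be repeated on a separate day", this time with the breathing instruction. That makes 12 sets per person. Under Measurements, thickness and sEMG are averaged over each set, so the analysed value is one mean per set.
- **Sample size.** "Considering an effect size of 0.3", "an alpha error probability of 0.05" and "a power of 0.80", "the estimated sample size is 30 participants". Then: "An additional 20% of the cohort will be recruited to compensate for the predicted sample size attrition". The total is at least 36.

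**The concern.** Repeated-measures ANOVA as SPSS normally runs it (the GLM procedure) needs every within-person cell filled. For objective 2, instruction is confounded with day by design, so the comparison needs both days: 2 x 6 = 12 cells per person and outcome. A set-wide failure, such as a lost ultrasound view or a failed electrode at one load, would remove the 11 sets successfully recorded for that outcome.

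The recruitment margin is described as cover for attrition, meaning people who are lost. If those losses occur, the margin is used up and any complete-case deletion comes out of the 30 that the power calculation needs. What is at stake is avoidable loss of power on objective 2, using data already collected.

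**Working it through.** **1. Reproduce the plan's figure.** Stated inputs: effect size 0.3, alpha 0.05, power 0.80. Assumed, because the plan does not give them: Cohen's f as the metric, one group, m = 6 levels, sphericity (epsilon = 1), and G*Power's Cohen effect-size option.

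Noncentrality = f² x N x (m − 1) = 0.09 x 30 x 5 = 13.5, with (m − 1) = 5 and (N − 1)(m − 1) = 145 degrees of freedom. Power is 0.806, and 30 is the smallest N that reaches 0.80. This matches the plan.

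**2. Check the attrition margin.** 30 x 1.2 = 36. Falling back to 30 is a loss of 6/36 = 16.7% of those recruited. A true 20% loss leaves 36 x 0.8 = 28.8, with power 0.786. (Covering a true 20% would need 30/0.8 = 37.5, so 38.) Attrition alone therefore costs about two points at most.

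**3. Add scattered missing sets.** Let p be the chance that any one set is missing, independently of the others. p is an assumption; the documents give no figure. The fraction of people with all 12 sets is (1 − p)^12. The power column applies the plan's own calculation from step 1 to the complete cases.

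| p | (1 − p)^12 | Complete of 30 retained | Power | Power if all 36 are retained |
|---|---|---|---|---|
| 0% | 1.000 | 30.0 | 0.806 | 0.883 |
| 1% | 0.886 | 26.6 | 0.746 | 0.834 |
| 2% | 0.785 | 23.5 | 0.682 | 0.777 |
| 5% | 0.540 | 16.2 | 0.487 | 0.580 |

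**4. What would using all available sets recover?** Step 3 uses a six-level load effect as its yardstick, so the instruction contrast was also simulated directly. Settings: 36 recruited, within-person correlation 0.5, effect set to give 80% power at n = 30, 1,500 runs, error about ±2 points.

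| Scenario | Complete cases | All available sets |
|---|---|---|
| 20% lost before day 2, no other gaps | 0.771 | 0.770 |
| 16.7% lost, plus 2% of sets | 0.678 | 0.787 |
| 16.7% lost, plus 5% of sets | 0.532 | 0.785 |

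A second simulation added person-by-day variation (SD 0.6 against a set-level SD of 1, instruction effect 0.5, 20% lost before day 2). It gave about 0.72 against 0.72 with attrition alone, 0.58 against 0.68 at 2%, and 0.43 against 0.70 at 5%. Only the gaps should be read from it. With those settings even 30 complete participants give only 0.73: the SD of the paired difference in day means is √(2 x 0.36 + 2 x 1/6) = 1.026.

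**5. If each day is analysed separately.** Only six sets must then be complete. At 2% this leaves 0.886 x 30 = 26.6 people, with power 0.746.

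**The case against.** The strongest reply is that the whole loss depends on a missing-set rate found nowhere in the documents. Participants are healthy, 15 minutes of rest separate the sets, and averaging 10 breaths means a few unreadable ones need not lose a set. This stands as a limit on size: at 0% there is no loss, and if all 36 stay, 1% is absorbed. It does not remove the deletion rule, nor protect against failure of a whole set.

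Second, the analysis is described as within each inspiratory protocol, which could mean a separate six-load ANOVA per day. Someone who missed day 2 would then stay in the day-1 analysis. That reading is open because the factors are not stated, but separate-day analyses would not test the with-and-without-instruction comparison in objective 2. It is also true that outcomes are analysed separately, so a lost sEMG set does not remove that person's ultrasound data.

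Third, repeated-measures ANOVA is an acceptable method for a small volunteer study. Agreed; the case for changing is that a better use of the same data is available at almost no cost.

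Three stronger readings are tempting and are not supported:
- **Predicted attrition itself leaves the study underpowered.** The plan raises recruitment from 30 to 36 for exactly this, and step 2 shows the margin is adequate to within about two points.
- **A mixed model would rescue people who miss day 2.** They carry essentially no information on the within-person instruction contrast under either method (0.771 against 0.770).
- **Complete-case analysis tilts results towards stronger participants.** Loads are percentages of each person's own MIP, so weaker people do not face a relatively heavier task. If gaps cluster at high loads the deletion may be selective, but the documents do not show that they do.

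**Conclusion.** The point holds as a weakness in the choice of analysis, worth correcting because the remedy is cheap. For objective 2, one missing set costs the person's other 11 for that outcome, and nothing in the sample size allows for this once the budgeted attrition has occurred. Under the assumed rates, complete-case power is about 0.75 (1% of sets missing), 0.68 (2%) or 0.49 (5%), against 0.806 with none missing. Using all available sets brings the simulated instruction contrast back to about 0.79 at both 2% and 5%.

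This rests on the standard listwise-deleting SPSS procedure, one two-day model for objective 2, independent missingness, and the reconstruction of N = 30 in step 1. The direction is secure whenever some sets are missing; the size cannot be fixed from the documents.

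**What to change.** For each outcome, make the primary analysis a linear mixed model fitted by REML to all available sets (MIXED in SPSS). Use fixed effects for instruction, load and instruction x load, and random effects for participant and participant-by-day. State that participants with some missing sets are kept. Retain the complete-case repeated-measures ANOVA, with its factors named, as a sensitivity analysis, and report the number of missing sets by load and day so that any clustering at high loads is visible.

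The cost is a rewritten Statistical analysis section and slightly more analysis work; no new data, participants or software are needed. The downside is reliance on a missing-at-random assumption, which should be stated.
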